#### **11.7.8 Other Safety Analyses**

The data collected from the ophthalmologic examination will be tabulated at each scheduled visit.

### **11.8 Other Analyses**

Not applicable.

### **11.9 Data Safety Monitoring Board**

An independent DSMB will be responsible for reviewing unblinded safety data in an ongoing manner and for monitoring and assuring overall safety of the study subjects. In accordance with an agreed-upon charter, the DSMB will meet periodically, on a regular

and/or ad hoc basis, to discuss and address any emerging safety or tolerability issues, including SAEs, discontinuations due to AEs, etc, as well as other relevant study information, such as recruitment status, ineligibility rates, and data quality. Based on any formal DSMB review meeting where blinded or unblinded safety data are reviewed and discussed, the DSMB will recommend to the sponsor one of the following:

- Continue the study without modification
- Continue the study but modify the protocol and/or ICF
- Suspend the study (or a cohort) until further notice, with recommendations for further action to address specific issues and appropriately managing active study subjects
- Terminate the study (or a cohort) with provisions for orderly discontinuation in accordance with GCP.

Modification, suspension or termination may be made for any of the following reasons:

- Concern about drug-induced liver injury
- Concern about suicide
- Any other safety concern

The approach to study (or cohort) modification, suspension, or termination will be described in the DSMB charter.

The sponsor will be notified of the DSMB's decision soon after the meeting. Minutes of all formal DSMB meetings and discussions will be maintained by the independent statistician, in a secure location, until completion or termination of the study, at which point they will be forwarded to Daiichi Sankyo for archiving.

### **11.10 Hepatic Adjudication Committee**

The HAC will comprise at least two qualified hepatologists, who are not investigators in the study and not otherwise directly associated with the sponsor. The HAC will follow its own charter for processing and adjudicating hepatic events. The HAC will adjudicate hepatic events in a blinded manner. This adjudication will be independent of the investigators. The HAC will complete assessments on an ongoing basis.

Adjudication of hepatic events will be based on evaluation of eCRFs and source documents, as available, including but not limited to hospital discharge summaries, diagnostic imaging, histopathology, consultation, and laboratory reports. Such patient's

relevant records will be provided to the HAC from the study sites according to HAC request.

### **11.11 Sample Size Determination**

Approximately 35 subjects with moderate and severe renal dysfunction will be enrolled in the study.

We need 30 subjects to observe at least 1 AE of moderate/severe dizziness and somnolence with 95% probability if the event rate is assumed to be 10%, which is nearly double of observed proportion in the Asian DPNP Phase 2 study (DS5565-A-J202).

Considering dropout, total of approximately 35 subjects will be enrolled into the study.

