## **2. STUDY OBJECTIVES AND HYPOTHESES**

### **2.1 Study Objectives**

#### **2.1.1 Primary Objective**

The primary objective is to characterise the safety and tolerability of DS-5565 in subjects with moderate to severe renal impairment.

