### 9.1 Adverse Events

#### 9.1.1 Definition of Adverse Event

An AE is any unfavorable and unintended sign (including an abnormal laboratory value or abnormal vital sign), symptom, or disease that develops after the subject signs the Informed Consent Form (ICF) and up to 7 days after the last dose of study medication (Visit 11), regardless of relationship to the investigational product.

Any symptom that the investigator or sub-investigator considers associated with DPN will be evaluated as an efficacy variable and will not be regarded as an AE. However, if the symptom is considered potentially related to the investigational product, such symptom will be regarded as an AE. If any pre-existing symptom or disease is aggravated during the study period, the aggravation will be reported as an AE, and the date of confirming the aggravation will be considered the date of event onset.

Dizziness, somnolence, edema, and weight increase are currently defined as “significant AEs”. Any other significant AEs to be added will be specified in the statistical analysis plan (SAP).

All antiepileptic drugs carry a risk of increased suicidal behavior and ideation. Furthermore, increased hepatic transaminases have been observed in the DS-5565 development program. Therefore, the following “suicidal behavior and ideation” and “liver enzyme elevations/liver dysfunction” will be treated as AEs of special interest.

- Increase in ALT or AST  $\geq 5 \times$  ULN
- ALT or AST rises to  $\geq 3 \times$  ULN and persists for more than 2 weeks
- Concurrent increases in ALT or AST  $\geq 3 \times$  ULN and T-Bil  $\geq 2 \times$  ULN
- ALT or AST  $\geq 3 \times$  ULN associated with a clinical presentation suggestive of liver injury (ie, including the appearance of fatigue, nausea, vomiting, jaundice, right upper quadrant pain or tenderness, fever, rash, and/or eosinophilia)
- Serious hepatobiliary AE
- Severe hepatobiliary AE

- Hepatobiliary AE leading to discontinuation
- Any transaminase elevation associated with a clinical presentation suggestive of liver injury
- An elevation of ALT or AST  $\geq 3 \times$  ULN (without clinical presentation suggestive of liver injury)
- AE related to suicide (if there are any “yes” responses to any of the questions in the C-SSRS)

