#### **9.1.2 Items to Be Investigated Concerning Adverse Events**

If an AE develops during the clinical study, the items in Table 9-1 will be investigated and the results will be recorded. The subject should be questioned in a general way, without asking about the occurrence of any specific symptoms.

Table 9-1: Items to be Investigated for Adverse Event

Items reviewed	Content of review	
Content of AE	Name of AE, date of onset	
Action taken regarding the investigational product	None	No change in investigational product dosage was made.
	Discontinued	The investigational product was permanently stopped.
	Permanently	
	Interrupted	The investigational product was temporarily stopped.
Outcome	Dose Reduced	The dosage of the investigational products was reduced.
	Classification of outcome, date of outcome assessment, date of resolution	
	Classification of outcome	
 
Recovered/Resolved
 

	Recovered/Resolved with Sequelae	
 
The subject fully recovered from the AE, with no residual effects observed.
 
The residual effects of the AE are still present and observable.
 
Identify sequelae/residual effects.
 

Severity	Not Recovered/Not Resolved	
 
Identify sequelae/residual effects.
 
The AE itself is still present and observable.
 

	Recovering/Resolving	
 
The AE was almost fully resolved, and the subject recovered to near-baseline status.
 

	Unknown	
 
No information and the outcome was unknown.
 

	Fatal	
Seriousness	Mild	Awareness of sign or symptom, but easily tolerated, ie, does not interfere with subject's usual function
	Moderate	Discomfort enough to cause interference with usual activity
	Severe	Incapacitating with inability to work or do usual activity, ie, interferes significantly with subject's usual function
Definition of SAE	Serious (according to the following definition of SAEs) / Not serious	
	
 
1. Results in death
 
2. Life-threatening
 
3. Requires inpatient hospitalization or prolongation of existing hospitalization
 
4. Results in persistent or significant disability/incapacity
 
5. A congenital anomaly/birth defect
 
6. An important medical event
 
	

Table 9-1: Items to be Investigated for Adverse Event (cont.)

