## **11.7 Safety Analyses**

### **11.7.1 Adverse Event Analyses**

All AEs will be coded using the Medical Dictionary for Regulatory Activities (MedDRA). Any AEs that appear after the first administration or that worsen relative to the pre-treatment state are considered as TEAEs.

The number and percentage of subjects reporting TEAEs will be calculated for the categories listed below by CrCL group and all-DS-5565 treatment. The number and percentage of subjects reporting TEAEs and ADRs will be summarized by system organ class, preferred term, and CrCL group and all-DS-5565 treatment.

- TEAE
- ADR
- Serious TEAE
- Serious ADR
- Severe TEAE
- Severe ADR
- Significant TEAE
- Significant ADR
- TEAE leading to treatment discontinuation
- ADR leading to treatment discontinuation

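### Does the study need a planned table for the moderate or severe dizziness and somnolence on which its size is based?

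*Combined protocol and SAP*

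**What the plan says.** Section 11.11 gives one quantitative basis for the size of the study: "We need 30 subjects to observe at least 1 AE of moderate/severe dizziness and somnolence with 95% probability if the event rate" equals 10%. That rate is described as close to twice the proportion seen in the Asian phase 2 study in DPNP. Enrolment is then raised to about 35 to allow for dropout; no dropout rate is stated.

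Section 11.7.1 sets out the adverse event reporting. "The number and percentage of subjects reporting TEAEs will be calculated for the categories listed below by CrCL group and all-DS-5565 treatment", and TEAEs and ADRs "will be summarized by system organ class, preferred term, and CrCL group and all-DS-5565 treatment". The categories are any, serious, severe, significant and leading to discontinuation, each for TEAEs and for ADRs.

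Two definitions matter here. Section 9.1.1 fixes the significant events: "Dizziness, somnolence, edema, and weight increase are currently defined as" significant, with no severity threshold. Table 9-1 in Section 9.1.2 grades every adverse event as mild, moderate or severe, and defines moderate as "Discomfort enough to cause interference with usual activity".

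Section 2.1.1 states the purpose: "The primary objective is to characterise the safety and tolerability of DS-5565 in subjects with moderate to severe renal impairment". Section 11.2 plans tables, figures and listings and leaves detailed methodology to an SAP still to be prepared. The supplied text contains no such SAP, so this assessment rests on the protocol.

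**The concern.** Safety is the primary endpoint, and moderate or severe dizziness and somnolence is the only event for which the protocol states a planning rate. A reader would expect the report to show how often it occurred. None of the outputs in Section 11.7.1 does so. Preferred-term rows include mild events, the significant category also adds edema and weight increase, and the severe category omits moderate events. Mild and moderate are not separated in any listed table.

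The line between mild and moderate also carries meaning for tolerability, because in Table 9-1 it is the point at which the event begins to disturb daily life. If the count could not be obtained, the report could not set the observed rate beside the assumed 10% or the phase 2 proportion behind it. In addition, Section 11.11 does not say whether the 10% applies to either event or to each.

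**Working it through.** **1. The plan's own figure.** Inputs from Section 11.11: rate p = 0.10 and required probability 0.95. The chance of at least one affected subject among n is 1 − (1 − p)^n.

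- Smallest n: ln(0.05)/ln(0.90) = 28.43, so 29.
- n = 28: 1 − 0.9^28 = 0.948
- n = 29: 1 − 0.9^29 = 0.953
- n = 30: 1 − 0.9^30 = 0.958
- n = 35: 1 − 0.9^35 = 0.975

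The stated 30 is correct with one subject to spare. Going from 30 to 35 allows for 1 − 30/35 = 14.3% dropout.

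**2. Either event or each.** A target of at least one event with a single 10% rate reads most naturally as one combined event, and 30 reproduces on that reading. The strictest alternative is that each event has a 10% rate, the two are independent (an assumption), and one of each must be seen:

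- n = 30: (1 − 0.9^30)² = 0.917
- n = 35: (1 − 0.9^35)² = 0.951

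The safety analysis set in Section 11.3 includes everyone who took at least one dose, so treated subjects who later drop out still count. On that basis 35 is a reasonable denominator, and even the strict reading reaches 95%.

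**3. What the planned outputs show about the target event.**

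| Output | Events counted | Relation to the target |
|---|---|---|
| Dizziness and somnolence by preferred term | any severity | upper bound for each term |
| Significant TEAE | four terms, any severity | looser upper bound |
| Severe TEAE, if shown by preferred term | severe only | lower bound for each term |
| Listings with recorded severity | each event with its grade | exact count |

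If both preferred-term rows are zero, the target event did not occur. If severe dizziness or somnolence appears, it did occur. If there are some events and none is severe, the tables leave the question open and the listings answer it. The exact count of moderate or severe cases always comes from the listings or the dataset, which for about 35 subjects is a short task.

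**The case for a change.** The strongest case for a change is that a count made after the fact leaves choices open: which MedDRA terms belong to each event, whether a subject is classified by maximum severity, and whether the result is for either event or for each. Section 9.1.1 sends only further significant events to the SAP, not a breakdown by severity, and no supplied text commits to one. A single table from data already collected would settle this at almost no cost.

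Part of this stands. No table listed in Section 11.7.1 reports the event, and a table by maximum severity would be useful. The stronger statement, that the target cannot be read out, does not stand, because the grade of every event is captured and listed. Nor does Section 11.11 set up an estimate: it asks for enough subjects to see the event, not for a rate to be tested or compared with 10%. It makes no promise for either renal function group separately, and it does not say that the severe category alone should carry the 95%. The remaining choices are ordinary table specifications, which belong in the SAP that Section 11.2 announces.

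**Conclusion.** No change to the plan is called for. The observation is accurate as far as it goes: the moderate-or-severe event used for sizing has no summary row among the tables in Section 11.7.1. This is missing table-level detail, not an error in design or analysis. The sample size is correct (29 needed, 30 stated, 95.8% at 30 and 97.5% at 35), and it still reaches 95.1% at 35 if both events must be seen. The planned counts are valid for what they describe, and the descriptive safety conclusion of this single-arm study would be the same with or without the extra row.

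This rests on three points: the 10% rate is taken as the plan's own assumption, severity is recorded as Table 9-1 requires, and the listings carry that grade. The 95.1% further assumes independence of the two events and all 35 subjects in the safety analysis set. The SAP was not available, so whether it already contains a severity table is unknown; the conclusion does not depend on it.

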## **12. DATA INTEGRITY AND QUALITY ASSURANCE**

The investigator/study site will permit study-related monitoring, audits, IRB review, and regulatory inspections by providing direct access to source data/documents. Direct access includes permission to examine, analyze, verify, and reproduce any records and reports that are important to the evaluation of a clinical study.

### **12.1 Monitoring and Inspections**

The monitor and regulatory authority inspectors are responsible for contacting and visiting the investigator for the purpose of inspecting the facilities and, upon request, inspecting the various records of the study (eg, CRFs, source data, and other pertinent documents).

The monitor is responsible for visiting study site(s) at regular intervals throughout the study to verify adherence to the protocol; completeness, accuracy, and consistency of the data; and adherence to International Conference on Harmonization (ICH) GCP and local regulations on the conduct of clinical research. The monitor is responsible for inspecting the CRFs and ensuring completeness of the essential study documents. The monitor should have access to subject medical records and other study-related records needed to verify the entries in the CRFs.

The monitor will communicate deviations from the protocol, standard procedures, GCP, and applicable regulations to the investigator and will ensure that appropriate action designed to prevent recurrence of the detected deviations is taken and documented.

The investigator agrees to cooperate with the monitor to ensure that any problems detected in the course of these monitoring visits are addressed and documented.

In accordance with ICH GCP and the sponsor's audit plans, this study may be selected for audit by representatives from the sponsor. Inspection of site facilities (eg, pharmacy, drug storage areas, laboratories, etc.) and review of study-related records will be performed in order to evaluate the conducting of the study and compliance with the protocol, ICH GCP, and applicable regulatory requirements.

### **12.2 Data Collection**

#### **12.2.1 Style of Data Collection**

##### **12.2.1.1 Case Report Form**

This study will use an Electronic Data Capture (EDC) system (Table 12-1) to generate CRFs, so the CRFs will be entered electronically. CRFs (including audit trails) will be

prepared for each subject. The eCRF will be completed, reviewed, and e-signed by the investigators. The EDC system will be validated prior to use.

Table 12-1: Electronic Data Capture System

Name of EDC system	Medidata Rave®
EDC system developer	Medidata Solutions Inc.
Entry method	Web-based data entry
Input terminal	Desktop computer at the study site
Incompatible operating systems	None
Recommended browsers	The Medidata Rave® supports any browser which is HTML 4, HTML 5, and CSS2 compliant. Browsers must have JavaScript enabled.
Screen Resolution	The minimum screen resolution required to properly display Medidata Rave applications is 1024 × 764.
Connection Speed	128kbps is the minimum connection speed recommended for using Medidata Rave.
Other	Adobe Flash Player : ver. 10 or above is required

### 12.2.1.2 Electronic Daily Diary

This study will use an Electronic Patient Report Outcome (ePRO) system (Table 12-2) to collect patient daily diary data. The device for electronic daily diaries (including audit trails) will be prepared for each subject. The electronic daily diaries will be completed by the patient and reviewed by the investigators. The ePRO system will be validated prior to use.

Table 12-2: Electronic Patient Report Outcome System

EDC system developer	eResearchTechnology, Inc
Entry method	Patient-reported outcomes; Hand-held device
Input terminal	DIARYpro® Mobile
Incompatible operating systems	None
Recommended browsers	DIARYpro® Mobile is a proprietary system that runs on a Windows platform. Windows OS and Internet Explorer 7.0, 8.0, 9.0, 10.0 or 11.0
Screen Resolution	N/A, as software is programmed to fit on the DIARYpro mobile device.

### 12.2.1.3 Other Reports

Results of pharmacokinetic test and laboratory tests are reported by central laboratory, separately. Procedures for these reports are set separately.

### 12.2.2 Preparation of Case Report Forms and Daily Diaries

All persons who make entries and/or corrections on CRFs or daily diaries should be trained and should be assigned their own accounts to use the EDC or ePRO system. The training record is regarded as a signature sheet.

1. CRFs will be created for subjects who sign the ICF for the study, and electronic daily diaries will be created for subjects who are conducted screening visit for the study.
2. The investigator or sub-investigator will prepare the CRF in accordance with CRF completion guidelines that are provided by the sponsor.
3. If study staff assists in the preparation of the CRF, they will do so under the direction of the investigator or sub-investigator.
4. The investigator will submit the CRF to the sponsor, and will keep a copy.
5. If there is a contradiction between some of the data that is entered in the CRF and the source documents, the investigator will prepare a separate record that explains the reason(s) for this discrepancy, and will submit that record to the sponsor.
6. Subject will receive the device for the electronic daily diaries and answer to the question.
7. The device for the electronic daily diaries should be collected when subject terminate

the study.

### **12.2.3 Signatures or Seals on the Case Report Form**

The investigator will confirm all of the CRFs that are prepared at that study site, and will enter his or her electronic signature in the file.

The investigator will also confirm all of the electronic daily diaries that are prepared at that study site.

### **12.2.4 Data Correction**

1. The investigator, sub-investigator, or study staff will correct the data in the CRF in accordance with the CRF completion guidelines that are provided by the sponsor.
2. The investigator will be responsible for the content of entries in the CRF.
3. Procedure for data correction of the electronic daily diaries will set separately.

## **12.3 Data Management**

Each subject will be identified in the database by a unique subject identifier as defined by the sponsor.

To ensure the quality of clinical data across all subjects and study sites, a Clinical Data Management review will be performed on subject data according to specifications given to Daiichi Sankyo. Data will be vetted electronically and/or manually as appropriate.

During this review, subject data will be checked for consistency, omissions, and any apparent discrepancies. In addition, data will be reviewed for adherence to the protocol and GCP. For eCRFs and ePRO data will be electronically vetted by programmed data rules within the application. Queries generated by rules and raised by reviewers will be generated within the EDC or ePRO applications and also resolved within the applications.

Data received from external sources such as central labs will be reconciled to the clinical database.

SAEs in the clinical database will be reconciled with the safety database.

All AEs will be coded using MedDRA.

## **12.4 Study Documentation and Storage**

### **12.4.1 Definition of Source Documents**

Source documents are original documents, data, and records from which the subject's CRF data are obtained. These include but are not limited to hospital records, clinical

and office charts, laboratory and pharmacy records, electronic diaries, microfiches, X-rays, and correspondence.

If the following items are entered directly into the CRF, the content of those CRF entries is defined as source data.

- 1) Direct entry of specific items (in the Comments column, etc.)
- 2) Entries such as "None" or "Unknown" for specific items
- 3) Reasons for use of concomitant drugs
- 4) Laboratory values that deviated from the reference range, if any, and reason for deviation.
- 5) Descriptions of AEs
- 6) AEs, if any, name of AE, severity, seriousness, outcome, relationship to the investigational product
- 7) Whether treatment was discontinued, and reason for discontinuation

#### **12.4.2 Storage**

All original source documents supporting entries in the eCRFs and electronic daily diary must be maintained and be readily available.

All essential documentation will be retained by the institution for at least 10 years after completion of the study (for a longer period if needed to comply with other applicable requirements), or until the institution is instructed otherwise by the sponsor.

No study document should be destroyed without prior written agreement between the sponsor and the investigator. Should the investigator wish to assign the study records to another party or move them to another location, he/she must notify the sponsor in writing of the new responsible person and/or the new location.

